**Figure 3.** During the high-resolution esophageal impedance measurement period after a 20-minute meal, under random allocation, both the healthy control group (a) and the patient group (b) demonstrated a significant reduction in the number of reflux events with diaphragmatic breathing. In contrast, the sham (normal) breathing group showed no significant difference in reflux events.

### **Research Purpose**

For patients with DGBI (Functional Gastrointestinal Disorders) who exhibit gastrointestinal symptoms that cannot identify organic causes after objective examinations, current treatment options are significantly limited. Dysregulation of the autonomic nervous system is one contributing factor. Abdominal breathing, by reducing respiratory frequency, promotes parasympathetic nervous system activity while inhibiting sympathetic nervous system activity. It is now officially recommended by

E6A0021096-10

international consensus conferences as an adjunctive therapy to alleviate symptoms of gastroesophageal reflux.

The purpose of this study is to investigate the autonomic nervous system responses through standardized autonomic nervous system monitoring, focusing on the impact of diaphragmatic breathing on the autonomic nervous system in both healthy subjects and patients with Functional Gastrointestinal Disorders (DGBI). Additionally, the study aims to confirm whether the implementation of diaphragmatic breathing can improve symptoms in DGBI patients, providing a basis for future reference in the treatment of DGBI patients.

### **Research hypothesis**

### Hypothesis 1: Diaphragmatic breathing can change Autonomic nervous system

Hypothesis 1-1 : Diaphragmatic breathing can increase the activity of the parasympathetic nervous system and decrease the activity of the sympathetic nervous system in healthy subjects.

Hypothesis 1-2 : Diaphragmatic breathing can increase parasympathetic nervous system activity and decrease sympathetic nervous system activity in patients with DGBI. E6A0021096-10 Total 30 Page, Page 20

### Hypothesis 2 : Diaphragmatic breathing can improve symptoms in patients with DGBI.

Hypothesis 2-1 : Introducing diaphragmatic breathing can improve symptoms in patients with Laryngopharyngeal Reflux Disease (LPR).

Hypothesis 2-2 : Introducing diaphragmatic breathing can improve symptoms in patients with Functional Dyspepsia (FD).

Hypothesis 2-3: Introducing diaphragmatic breathing can improve symptoms in patients with Irritable Bowel Syndrome (IBS).

### H. Research methods, procedures, and execution progress.

- 1.Please elaborate on the research methods adopted in this project and the reasons behind their selection.
- 2. Anticipated difficulties and possible solutions.
- 3. If it is a consecutive project, please also attach the annual research progress report or primary data for the corresponding year.

### **Research Methods**

### Participant

The trial is expected to last for 1 year, with a research period ending on December 31, 2024. It aims to recruit 600 participants, including 150 healthy volunteers to be solicited through advertisements. Additionally, 150 participants with Laryngopharyngeal Reflux (LPR) will be recruited from the Gastroenterology Outpatient Department, along with 150 participants with Functional Dyspepsia (FD) and 150 participants with Irritable Bowel Syndrome (IBS). The inclusion and exclusion criteria for participants are as follows :

### **Inclusion Criteria for Participants :**

### Inclusion criteria for healthy subjects :

- 1. Aged between 18 and 70 years old, clear consciousness, and willing to sign the informed consent form for the study.
- 2. Without any gastrointestinal symptoms or the use of gastrointestinal medications.

### Inclusion criteria for Laryngopharyngeal reflux disease subject :

- 1. Aged between 18 and 70 years old, clear consciousness, and willing to sign the informed consent form for the study.
- 2. The definition of Laryngopharyngeal Reflux (LPR) is characterized by the presence of symptoms lasting for more than three months, including hoarseness, a sensation of a lump in the throat, chronic cough, and frequent throat clearing. These symptoms occur at least once a week. Diagnosis is confirmed through a standardized LPR assessment questionnaire (Reflux Symptom Index RSI), which consists of nine reflux-related symptoms. Each symptom is rated on a severity scale from 0 (asymptomatic) to 5 (most severe). If the total score exceeds 13 points, the patient meets the criteria for Laryngopharyngeal Reflux.

### Inclusion criteria for Functional dyspepsia subject :

- 1. Aged between 18 and 70 years old, clear consciousness, and willing to sign the informed consent form for the study.
- 2. Those who meet the FD definition Functional dyspepsia is characterized by chronic (occurring at least once a week, lasting for a minimum of three months, with the first symptoms manifesting at least six months ago) upper gastrointestinal symptoms (any of the following): postprandial bloating, a tendency to feel full easily, upper abdominal pain or a burning sensation, without symptoms of gastrointestinal bleeding or significant weight loss, and with no abnormalities found upon upper gastrointestinal endoscopic examination.

### Inclusion criteria for Irritable bowel syndrome subject :

- 1. Aged between 18 and 70 years old, clear consciousness, and willing to sign the informed consent form for the study.
- 2. Those who meet the definition of IBS. Irritable bowel syndrome (IBS) is a chronic condition characterized by lower gastrointestinal symptoms occurring at least once a week and lasting for a minimum of three months. These symptoms include abdominal pain accompanied by either diarrhea or constipation, without any signs of gastrointestinal bleeding or significant weight loss. Individuals with IBS exhibit no abnormalities upon examination through colonoscopy.

### **Exclusion Criteria for Participants :**

- 1. Pregnant or lactating women.
- 2. Infection currently undergoing antibiotic treatment.
- 3. In the past two months, underwent tracheal intubation.
- 4. Those with myocardial hypoxia or who have recently experienced a myocardial infarction.
- 5. Unable to collaborate.

### **Research Process Diagram**

### **Finish experiment**

### **Research Steps**

The subjects who meet the inclusion criteria of this study will undergo an initial assessment of heart rate variability and psychosomatic symptoms after enrollment. Subsequently, a two-week

experiment will be conducted, during which the subjects will receive one session of diaphragmatic breathing training by the researchers. After the guided training, the subjects will undergo another assessment of heart rate variability. In the first week, participants will engage in self-practice of the instructed content twice daily, each session lasting 5 minutes, and will record a weekly diaphragmatic breathing diary.

After the first week, subjects will undergo another assessment of heart rate variability and psychosomatic symptoms. In the second week, participants will continue daily self-practice with two sessions of instructed content, each lasting 5 minutes, and will maintain a diaphragmatic breathing diary. Following the second week, subjects will undergo a final assessment of heart rate variability and psychosomatic symptoms, completing the experiment.

Researchers recommend spending approximately 15 minutes on diaphragmatic breathing training, 15 minutes on measuring heart rate variability, and approximately 20 minutes for questionnaire completion. The measurement of heart rate variability utilizes a non-invasive device called "LEADTEK" portable electrocardiogram recorder (Ministry of Health and Welfare Medical Device Manufacturing License No. 006972). If participants have any questions or concerns during the abdominal breathing training process, they are encouraged to contact the researchers.

### **Diaphragmatic Breathing (It takes about 15 minutes)**

- 1. Sit in a comfortable place and close your eyes.
- 2. Place one hand on the chest and the other hand on the abdomen to practice diaphragmatic breathing: During diaphragmatic breathing exercises, the hand on the abdomen will rise with inhalation and fall with exhalation, while the hand on the chest remains stationary.
- **3.** Inhale through the nose for about 4 seconds, feeling the expansion of the abdomen. (Upon the first inhalation, there may be a slight sense of tension.)
- **4.** Hold your breath for 2 seconds.
- **5.** Exhale slowly and steadily through the mouth for approximately 6 seconds, keeping the mouth relaxed throughout the process.
- 6. Repeat this breathing cycle for 5 minutes.

### ANS Protocol (It takes about 15 minutes)

The ANS Protocol is a standardized and validated method used to assess the autonomic nervous system's (ANS) responses to baseline conditions and stress stimuli. It consists of three stages: a resting phase (5 minutes), a mental arithmetic test under stress conditions (3 minutes), and a recovery period (5 minutes) during which heart rate variability (HRV) is measured. The mental arithmetic test involves subjects performing continuous subtraction of 7 from a randomly generated four-digit number using mental calculation only. If an error occurs, the process is restarted, and the entire procedure lasts for 3 minutes.

ANS Detection Steps :

- 1. Confirm that the status indicator light is in a measurable state (LED color: green), and then attach the electrode patches. •
- 2. R (Red dot): Please paste on the inner side of the right wrist.
- 3. L (Yellow dot): Please paste on the inner side of the left wrist.
- 4. F (Green Marking): Please paste on the inside of the left wrist.
- 5. Press the measurement button on the device to initiate the measurement.
- 6. Before the formal commencement of measurements, the device will conduct a preliminary signal quality check. Participants are advised to remain still and refrain from engaging in conversation during this process.
- 7. The measurement officially begins at 7: Please instruct the subjects to remain still and refrain from talking, waiting quietly for 3 to 5 minutes until the measurement is completed. •
- 8. Measurement Completed: Display Measurement Results.

The HRV indicators for assessing the ANS are as follows : 

- 1. Time Domain Indicators
  - The square root of the mean of the sum of the squares of the Successive differences (RMSSD) : Assessing Parasympathetic Nervous System Activity

### 2. Frequency Domain Indicators

- ♦ Low frequency power (LF) : Assessing Sympathetic Nervous System Activity
- ♦ High frequency power (HF) : Assessing Parasympathetic Nervous System Activity
- ♦ Low-frequency/High-frequency Power Ratio (LF/HF ratio) : Assessing the balance of the sympathetic and parasympathetic nervous systems.

### **Questionnaire Evaluation Tool (It takes about 20 minutes)**

Disease Questionnaire Assessment :

- Gastroesophageal Reflux Disease Questionnaire (GERDQ) The questionnaire score exceeding 12 points indicates a high likelihood of having GERD.
- Reflux Symptom Index (RSI)  The nine reflux-related symptoms are graded on a severity scale from 0 (no symptoms) to 5 (most severe), and a total score exceeding 13 indicates a higher probability of suffering from laryngopharyngeal reflux.
- Functional Dyspepsia (FD) The subjective assessment revolves around symptoms and quality of life, primarily including postprandial fullness, early satiety, and upper abdominal bloating as digestive discomfort symptoms. Each item is scored from 0 to 6 points, with 0 points indicating no symptoms and 6 points indicating extremely severe symptoms. The total score ranges from 0 to 52 points, with higher scores indicating more severe symptoms.
- Irritable Bowel Syndrome (IBS) Diagnostic criteria reference Rome IV, The main symptoms began at least 6 months ago, with recurrent abdominal pain occurring at least once a week on average in the past three months. Additionally, at least two of the following symptoms are present: abdominal pain related to bowel movements, changes in bowel frequency, and alterations in the appearance of stool.
- Gastrointestinal Symptom Rating Scale (GSRS) Applicable to the general population with gastrointestinal symptoms for measurement and evaluation of treatment effectiveness, using a Likert 4-point scoring system. Positive scoring is employed, where higher scores indicate greater severity of symptoms, and lower scores represent higher levels of health.

Physical and Mental Stress Questionnaire Assessment :

- Pittsburgh Sleep Quality Index (PSQI) 41 is not only suitable for evaluating sleep quality of patients with sleep disorders and mental disorders, but also suitable for the evaluation of sleep quality of ordinary people. 18 items are composed of 7 components, each component is scored on a scale of 0-3, and the total score ranges from 0-21 points. The higher the score, the worse the sleep quality.
- Taiwanese Depression Scale (TDQ) 42 includes three parts: emotion, cognition and body, with a total of 18 questions, and the scale is scored on a four-point scale. Each question is scored on a scale from 0 to 3, and the total score ranges from 0 to 54 points. Those with a score greater than 18 indicate depressive symptoms.
- State-Trait Anxiety. Inventory (STAI) 43 includes two subscales, the Situational and Trait Anxiety Scale, with a minimum score of 20 and a maximum score of 80, with higher scores representing anxiety symptoms.
- The Perceived Stress Scale (PSS-10) 44 is to evaluate the degree of stress in personal life situations, and the higher the score, the greater the stress.
- Esophageal Hypervigilance and Anxiety Scale (EHAS) 41 Esophageal hypervigilance and anxiety can cause symptoms in patients with chronic esophageal diseases, including gastroesophageal reflux, esophageal atlasia and functional esophageal diseases. The questionnaire contains 15 items and can be divided into two main categories . Section: Symptoms of Esophageal Hypervigilance and Symptoms of Esophageal Anxiety. This questionnaire can not only assess the sensory system symptoms of any esophagus-related diseases, but also assist in the diagnosis of functional esophageal diseases.
- Laryngeal Hypervigilance and Anxiety Scale (LHAS) 41 Throat hypervigilance and anxiety can trigger symptoms in patients with chronic esophageal disease. The questionnaire contains 15 items and can be divided into two main parts: throat hypervigilance symptoms and throat anxiety symptoms. This questionnaire can not only assess the sensory system symptoms of any esophagus-related diseases, but also assist in the diagnosis of functional esophageal diseases.
- Visceral Sensitivity Index (VSI) 45 measures anxiety specific to the gastrointestinal tract. It includes 15 items, with a minimum score of 0 and a maximum of 5 points for each item, and a minimum score of 0 and a maximum score of 75 points for the total score.

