### **Statistical Analysis**

If a continuous variable follows a normal distribution, it is represented by the mean and standard deviation; if it does not follow a normal distribution, it is represented by the median and interquartile range. The treatment effectiveness is presented as the improvement percentage based on the pre- and post-treatment sleep habit questionnaire, depression questionnaire, anxiety questionnaire, stress questionnaire, digestive symptom questionnaire, and irritable bowel syndrome questionnaire. The efficacy of diaphragmatic breathing was assessed using a Chi-squared test to compare percentages. A P-value less than 0.05 was considered statistically significant. The statistical analysis software used is SPSS 19 (SPSS, Inc, Chicago, IL, USA).

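### The effectiveness list names no clear LPR symptom score, and if its IBS questionnaire is the unscored Rome IV criteria, that outcome is poorly suited to a two-week before-after comparison

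*Protocol*

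**What the plan says.** Hypothesis 2 has three parts, one per patient group. Part 2-1 reads "Introducing diaphragmatic breathing can improve symptoms in patients with Laryngopharyngeal Reflux Disease (LPR"); parts 2-2 and 2-3 say the same of FD and IBS. The Participant section plans 150 patients in each group.

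The Statistical Analysis section presents effectiveness as an improvement percentage, before against after treatment, on six tools: "sleep habit questionnaire, depression questionnaire, anxiety questionnaire, stress questionnaire, digestive symptom questionnaire, and irritable bowel syndrome questionnaire". Percentages are compared with a Chi-squared test.

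The tools are described under Questionnaire Evaluation Tool:

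- **LPR.** RSI is collected. The LPR inclusion criteria also use it for entry, as the "standardized LPR assessment questionnaire (Reflux Symptom Index RSI), which consists of nine reflux-related symptoms", each graded 0 to 5, with a total above 13 qualifying.
- **Throat-specific scale.** The Laryngeal Hypervigilance and Anxiety Scale (LHAS) covers "throat hypervigilance symptoms and throat anxiety symptoms".
- **IBS.** The only IBS-labelled entry is a set of Rome IV diagnostic criteria with three elements: "The main symptoms began at least 6 months ago"; "recurrent abdominal pain occurring at least once a week on average in the past three months"; and "at least two of the following symptoms are present", the choices being a link between pain and bowel movements, changed bowel frequency and changed stool appearance. No item score, total or range is given.
- **FD.** Each item is scored 0 to 6, with a stated total of 0 to 52.
- **General.** The Gastrointestinal Symptom Rating Scale (GSRS) is a graded scale described as usable for evaluating treatment.

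The IBS inclusion criteria ask for "lower gastrointestinal symptoms occurring at least once a week and lasting for a minimum of three months" and set no minimum time since onset. Research Steps places symptom assessments at baseline, after week 1 and, finally, after week 2.

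**The concern.** A reader of the analysis text cannot tell which scale answers Hypothesis 2-1. None of the six labels mentions reflux, larynx, throat or RSI, although RSI is the obvious candidate and is already collected.

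For Hypothesis 2-3 the label is specific, but the only tool matching it is a diagnostic definition. Such criteria are met or not met, so an improvement percentage could only count patients who cease to meet them. One element concerns the date of onset, and another averages pain over three months, while follow-up lasts two weeks. A real benefit over two weeks could go largely unrecorded on the pain element, although graded scales are filled in at the same visits.

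Two of the three symptom hypotheses are touched, covering 150 + 150 = 300 of the 450 planned patients. In addition, the two IBS definitions disagree on onset, and the FD score range is arithmetically impossible.

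**Working it through.** The protocol gives no figure of its own on this point, so there is nothing to reproduce.

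**1. Matching labels to tools.** Sleep, depression and stress point to the PSQI, TDQ and PSS-10. Anxiety points to the STAI, or loosely to the EHAS, LHAS or VSI. The digestive symptom label could mean the FD score, GSRS, GERDQ or RSI. The IBS label matches only the Rome IV entry. No label clearly yields an LPR symptom score. LHAS does not fill the gap, because it measures hypervigilance and anxiety rather than symptom severity. RSI would: 9 items × 5 = a maximum of 45.

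**2. The pain element, if Rome IV status is the outcome.**

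Inputs from the protocol: a three-month window and a threshold of one episode a week (Questionnaire Evaluation Tool); assessments at 7 and 14 days (Research Steps).

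Assumptions: three months is 91 days (12 weeks as a check), the baseline rate *f* per week is constant, and recall is even over the window.

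- Share of the window before treatment: week 2, (91 − 14)/91 = 77/91 = 85%; week 1, 84/91 = 92%. With 12 weeks, the week-2 share is 10/12 = 83%.
- With a proportion *r* of pain relieved over *d* days, the recalled average is *f* × (91 − *d* × *r*)/91. It falls below 1 only if *f* < 91/(91 − *d* × *r*).
- Week 2, complete relief: 91/77 = 1.18 (12-week window: 12/10 = 1.20). Week 2, 50% relief: 91/84 = 1.08.
- Week 1, complete relief: 91/84 = 1.08. Week 1, 50% relief: 91/87.5 = 1.04.
- Patients pain-free for all 14 days, with illustrative baseline rates: 2 × 77/91 = 1.69; 3 × 77/91 = 2.54; 5 × 77/91 = 4.23 per week. All still meet the element.
- Pain-free days needed to come down to one a week, 91 × (1 − 1/*f*): 45.5 for *f* = 2, 60.7 for *f* = 3 and 72.8 for *f* = 5, so about 46, 61 and 73 days against 14 available.

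**3. The other two elements.** Elapsed time can only turn the onset element from not met to met, so it cannot improve. The two-of-three features have no stated window, so a patient could leave the criteria by that route; the protocol gives nothing from which to size this.

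**4. Onset, set side by side.** The IBS inclusion criteria require three months of symptoms and no minimum time since onset. The Rome IV entry requires onset at least 6 months ago. The FD inclusion criteria do carry a six-month onset rule. An IBS patient with onset 3 to 6 months before entry can therefore be enrolled without meeting the Rome IV entry at baseline. If that entry is the outcome, such a patient cannot show improvement on it.

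**5. FD range.** With every item scored 0 to 6 and summed, the maximum must be a multiple of 6. But 52/6 = 8.67; eight items give 48 and nine give 54.

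**The case against.** The strongest reply is that the IBS part depends on a reading the protocol never states. The Rome IV entry is introduced as diagnostic and has no score, which fits poorly with an improvement percentage. In the same list, GSRS is described as a tool for evaluating treatment. An unnamed IBS form, or GSRS itself, could be what is meant. This stands, so the insensitivity argument is conditional. It does not remove the point: if another tool is meant, the protocol does not identify it as the IBS questionnaire.

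Second, the digestive symptom label may already include RSI, and mapping labels to scales can be left to an SAP, which is not at hand. A reader might infer that LPR symptoms have been dropped from the efficacy analysis. The documents do not support that: RSI is fully described and nothing excludes it. What remains is that the section itself lists the effectiveness tools, in labels that do not settle the matter.

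Third, the arithmetic uses illustrative pain rates and even recall, and covers one element of three. That is correct. A reader might infer that almost no IBS patient could register improvement. The protocol gives no baseline pain frequency, no window for the two-of-three features and no distribution of onset, so no such proportion follows.

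Fourth, RSI change has a weakness of its own. LPR patients are selected on RSI above 13, and the Research Steps text describes no comparison arm, so some fall in RSI is expected from regression to the mean. This also stands and belongs with the fix.

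**Conclusion.** The point holds in a limited form and should be fixed; confidence is medium.

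- **Without any inference:** the effectiveness list names no clear LPR symptom score; the two IBS definitions conflict on onset; and the FD total of 52 cannot arise from items scored 0 to 6.
- **Conditionally:** if the IBS questionnaire is the Rome IV entry, which is the natural reading because no other tool carries that label, the outcome is poorly suited to a two-week comparison. The onset element cannot improve. The pain element registers complete relief at week 2 only for patients below about 1.2 episodes a week. This rests on a window of 12 or 13 weeks, a constant baseline rate and even recall.

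The documents do not establish that Rome IV status is the intended outcome, that it could never change, or how many patients would be affected.

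**What to change.** In the Statistical Analysis section, name one scale per hypothesis, with change from baseline to week 2:

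- **2-1:** RSI total.
- **2-2:** the FD score.
- **2-3:** a graded symptom score already collected. GSRS is the candidate, once its suitability for IBS is confirmed; the validation cited for it was done in reflux patients.

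Check first that the recall periods of all three scales, which the protocol does not give, fit assessments one and two weeks apart. State how a change score relates to the planned improvement percentages and Chi-squared test. Keep Rome IV for diagnosis only. Say which tool the digestive symptom label means. Reconcile the onset wording of the IBS inclusion criteria with that of the Rome IV entry, and correct either the FD item range or its total.

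The cost is mainly wording, since the scales are already in the battery and no visit or questionnaire is added. There are three downsides. IBS diagnostic status is no longer an efficacy outcome. GSRS is a general scale and less specific to IBS. RSI change in patients selected on RSI above 13 is open to regression to the mean, so an uncontrolled before-after change should not by itself be reported as treatment benefit.
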